Over the past decade, improvements in immunosuppressive regimens, surgical techniques, and organ procurement have resulted in a significant increase in renal transplantation success (Oniscu et al, 2005). Currently, the worldwide rates for 1- and 5-year graft survival are 95% and 80%, respectively, with death with a functioning graft being the most common reason for renal graft loss after 1 year (Daly et al, 2005). Studies on renal transplantation outcomes have traditionally focused on patient and graft survival, with little to no consideration of graft function (Boom et al, 2000). Although graft loss is the worst type of graft dysfunction, grafts with an impaired function require the most intense follow-up, are economically most costly and require rigorous clinical management to preserve life-expectancy of the graft (Boom et al, 2000). For these reasons, parameters of graft function are being increasingly included as outcome measures in renal transplantation studies, including delayed graft function (DGF). Indeed, the new UNOS allocation policies

(http://optn.transplant.hrsa.gov/policiesAndBylaws/policies.asp) scheduled for implementation in 2014 will tend to give higher risk kidneys to older diabetic recipients. This is likely to increase the risk significantly for DGF and poorer allograft function.

Despite a decline in the number of patients experiencing allograft rejection episodes over the past decade, the incidence of patients with DGF has remained steady and was reported in 2.6 percent of transplants from living donors, compared to 22, 28, and 41 percent of SCDs, ECDs, and donations after cardiac death patients respectively.

[figure not shown]

Figure 1: Data obtained from United States Renal Data Systems Report Transplantation 2012 Vol 2, pp 283-294.

Most deceased donor and some live donor organ transplants manifest a degree of early dysfunction (Halloran and Hunsicker, 2001). Delayed graft function (DGF) is a term used to describe the lack of acceptable function in a kidney after transplantation (Daly et al, 2005). DGF has been well described in association with an inferior functioning kidney at 1 and 2 years post-transplant (Halloran et al, 1988; Hariharan et al, 2003). Typical histological findings of DGF are dilatation of tubules, loss of proximal epithelial cell brush border, epithelial cell necrosis/apoptosis, and cellular casts (Smith et al, 2003). In the presence of DGF, kidneys are more likely to have adverse outcomes including decreased functional graft survival and 6-month patient survival, and increased acute rejection (Daly et al, 2005; Halloran and Hunsicker, 2000). It is interesting to note that analyses of the UNOS scientific renal transplant registry (United States) showed DGF was associated with increased probability of patient death in the first 6 months (Halloran and Hunsicker, 2000), whereas analyses in the Netherlands found DGF to be an independent risk factor for acute rejection and suboptimal renal function at 1 year, but not survival (Boom et al, 2000). The use of kidneys from extended criteria deceased donors (ECD) are also associated with higher rates of DGF and poorer long-term survival. These findings are especially important in view of recent publications which showed compromised outcomes in patients receiving kidneys from suboptimal donors. A recent analysis of outcomes from 9134 recipients of cardiac-death and brain-death donor kidneys, donor age ≥60 years was identified as a risk factor for graft failure and reduced long-term renal function. (Summers et al, 2010). These investigators found that graft survival and renal function decrease as the age of the donor increases, with recipients of these ECD kidneys having twice the risk of graft failure compared with recipients of younger donor kidneys. Another group performed a comprehensive systematic review of kidney transplants from ECDs and concluded that management protocols for this patient population need to be based on nephronprotecting strategies (Pascual et al, 2008). Thus strategies to reduce IRI and DGF are critical to increasing the number and long-term outcomes of marginal kidneys.

Historically DGF has been defined as the requirement for dialysis during the first week after renal transplantation, however the postoperative requirement of hemodialysis or peritoneal dialysis is not standardized and the decision to

dialyze varies from center to center and among consultants (Daly et al, 2005). More recently, efforts have been made to scientifically quantify DGF in a more stringent manner with various alternative definitions of DGF including; (1) the number of days to achieve a creatinine clearance of >10 mL/min, calculated by the Gault-Cockroft formula (Giral-Classe et al, 1998), (2) a serum creatinine level of >3 mg/dL on the fifth day post-transplant (Humar et al, 2000), (3) the need for dialysis within 72 hours after transplantation (Hetzel et al, 2002), (4) serum creatinine level changes, including an increase, remaining unchanged, or decreasing by less than 10% per day immediately after surgery during three consecutive days for >1 week (Boom et al, 2000), (5) a rising serum creatinine level above that before surgery, or urine output of <300 mL within 6 hours of transplantation, despite diuretics and adequate volume (Gonwa et al, 2002), (6) urine output of <1 L in the first 24 hours or a decrease in serum creatinine of <20-30% reflected in a poor glomerular filtration rate (GFR) (Halloran and Hunsicker, 2001), and (7) calculating the creatinine reduction ratio on day two following surgery (Salahudeen et al, 2004). However despite these alternative suggestions, the conventional definition of "requirement for dialysis in the first week post-transplant" remains the most utilized and published definition for DGF, with "need for dialysis" being easily measured and clinically relevant.

The reported incidence of DGF varies widely depending on the source of the graft, with DGF estimated to occur in approximately 20-35% of all patients who receive a deceased donor graft (Koning et al, 1997; Halloran and Hunsicker, 2001), and rates varying up to 80% in association with extended criteria (ECD) donor grafts ([name] personal data from CSMC). The risk factors for DGF are the same as those that influence graft survival and include donor tissue quality (age), brain death and other components of cadaver donation, preservation variables particularly cold ischemia time, immune variables, and recipient variables (Halloran and Hunsicker, 2001). The duration of cold ischemia time has been shown to have a direct effect on the presence of DGF and graft survival with durations longer than 28 hours associated with increased risk (Lechevallier et al, 1998; Jacobs et al, 1996; Peters et al, 1995; Kahan et al, 1987), and a 23% increase for every 6 hours of cold ischemia time (Ojo et al, 1997). Additionally, DGF is significantly associated with the use of kidneys from older donors, particularly donors of more than 50 years of age (Boom et al, 2000). In the United States, in the last decade, the proportion of deceased donors

older than 50 years of age has increased from 21% to 30% (Nathan et al, 2003; Ojo et al, 2001), however the kidney waiting list has increased by 260% and the number of deceased donor kidney transplants has increased by only 16% (Metzger et al, 2003; Port, 2001; Nathan et al, 2003). Due to the increasing disparity between organ supply and demand, the use of kidneys from "older" expanded criteria donors (ECDs) has become generally accepted and increasingly common (Metzger et al, 2003).

In the United States, the United Network for Organ Sharing (UNOS) (www.unos.org) which administers the national Organ Procurement and Transplantation Network (OPTN) (www.optn.org) defines two types of deceased donor kidneys, namely "standard criteria donors" (SCD) and "expanded criteria donors" (ECD). Using pre-transplant variables to identify increased risk of graft loss, an ECD donor kidney is defined as a kidney donated for transplantation from (1) a brain-dead donor over the age of 60 years, or (2) from a donor between the ages of 50-59 with at least two of the following: a history of hypertension, a terminal serum creatinine greater than or equal to 1.5 mg/dl (normal range 0.8-1.4 mg/dl), or death from a cerebral vascular accident (CVA) (stroke or aneurysm). In comparison, an SCD donor kidney is defined as a kidney donated for transplantation by a donor who has suffered brain death and does not fit the criteria for ECD. With the growing demand for first-time and repeat deceased donor renal transplants, ECD donor kidneys are being increasingly considered by transplant programs. As a consequence of the utilization of marginal kidneys, DGF is a major complication following transplantation with ECD donor kidneys.

Complement as a Mediator of Ischemia Reperfusion Injury (IRI)

The complement system in humans exists as a system of recognition molecules, proteolytic enzymes and receptors for activated complement components that are responsible for host defense. The complement system can be activated in at least 3 separate ways; first, the classical pathway which depends on antibody binding to antigen targets and binding complement components (i.e. Clq) to ultimately activate C3 and initiate terminal complement component activation of C5b-C9 (see figure 1). Binding of lectins (i.e. mannose binding lectin and mannose binding lectin serine protease (MBLSP) activate the C3 convertase without activation of C1->4->2 (C3 convertase). In addition, the alternative pathway is activated by interaction with $\rm H_2O$ or activating surfaces. The deposition of complement on

bacteria or sites of injury signal initiation of an inflammatory response and tags complement bound targets for elimination through apoptosis or phagocytosis by macrophages. The complement system also contains a number of receptors that modify or abate complement-mediated inflammation. Complement also exists in two distinct compartments (central and local). The central compartment of complement is produced in the liver and is responsible for all circulating complement factors. The peripheral compartment included complement generated locally in organs such as the CNS and kidneys (Sacks et Zhou 2012. Activation of complement in the peripheral compartments appears to be regulated primarily by IRI. Figure 2 below describes the importance of complement activation in initiation of renal tubular cell (RTC) injury with reference to induction by IRI. Briefly, IRI stimulates C3 production in the RTCs that is subsequently cleaved by the MBL/MBLSP or alternative pathway (Sacks et Zhou 2012). C3b generated then activates C5 to C5a and C5b. C5b forms the C5b-C9MAC which induces cell death and cytokine (IL-6) release. C5a interacts with the C5aR to induce apoptosis and cell death. Data from (Sacks et Zhou 2012) have also shown that kidneys from C3 deficient mice are resistant to IRI. Other investigators have also shown that expression of C3 and other complement components in human donor kidneys before transplantation had a negative impact on graft outcome at 2-3 years (Naesens et al 2009). Thus there is significant support for a role of complement activation in inducing RTC injury and ultimately DGF and it would be reasonable to assume that administration of complement inhibitors would be of potential benefit in prevention or amelioration of RTC injury and possibly improve outcomes in kidneys at high risk for development of DGF.

[figure not shown]

Figure 2 shows complement activation by I/R injury (from Sachs & Zhou 2012).

Evidence for Use of Clinh to Prevent IRI and DGF

Although limited, there are recent investigations which show dramatic results in prevention of IRI after C1INH treatment. (Dalle Lucca et al 2012) investigated the ability of recombinant C1INH (rC1INH) to alter tissue injury in a porcine model of controlled hemorrhage. In this model, the administration of 100U/kg or 250U/kg rC1INH significantly reduced IRI injury to kidneys, lungs, intestine and liver. The animals treated with 250U/kg also showed significant reductions in TNF- α levels and severity of metabolic acidosis. The significant beneficial effects of rC1INH administration were found to be related to the ability of C1INH to reduce IRI induced complement activation in tissue. All treated animals also showed reduced immune cell infiltration and cytokine production. The authors felt that the use of rC1INH would have significant benefits in patients with hemorrhagic shock in prevention of IRI and organ failure (Castellano et al, 2010). In a comprehensive analysis of rC1INH use in an IRI model of kidney injury in the swine model found that IRI was associated with significant C3 activation, primarily through the MBL/MBLSP-2 pathway. The infusion of rC1INH led to significant reductions in peritubular capillary C4d deposition, and C5b-C9MAC. Complement inhibition with rC1INH also reduced the numbers of infiltrating CD163+, CD4+ and CD8+ T-cells. Animals treated with rC1INH had significantly less RTC injury and renal damage. The authors conclude that the use of C1INH may represent a novel therapeutic approach in the prevention of DGF that would have particular relevance to kidney transplantation.

2.0 Hypothesis

Since complement activation is detectable in animal models of IRI and in human kidneys after IRI and since experimental data suggests that use of C1INH prior to induction of IRI shows significant beneficial effects on reducing IRI as well as inflammatory cell infiltrates, we hypothesize that the use of C1INH in patients receiving deceased donor (DD) kidney transplants with high risk for DGF will show significant reductions in DGF and improved outcomes post-transplant compared

with patients receiving DD transplants who do not receive C1INH treatment.

2.1 Study Objectives

In this study, we propose to investigate the application of preoperative and post-transplant doses of C1INH (Berinert®)vs. placebo in adult subjects receiving a deceased donor renal allograft considered at high-risk for IRI and DGF. We hypothesize that C1INH treated patients will demonstrate improved function of the kidney allograft compared to placebo, with equivalence in safety. We will also evaluate biopsies at transplant in all entered patients.

The primary objectives of this study are: Using a double blinded, placebo controlled format, we will:

- 1. Evaluate and compare the safety of C1INH (50 U/kg, round to the nearest 500unit) administered pre-transplant and 24 hrs post-transplant in recipients of kidney allografts from high risk deceased donors. The secondary objectives are to:
- 1. On the basis of safety and efficacy, determine appropriate Berinert® study dose for Phase III investigation, and
- 2. Determine appropriate endpoint choice for Phase III investigation.

2.2 Study Synopsis

INVESTIGATIONAL AGENT	A Phase I/II, Double-Blind, Placebo- Controlled Study: Assessing Safety and Efficacy of Intraoperative and Post- Transplant C1 Inhibitor(Human) (C1INH)vs. Placebo in Recipients of a Kidney Allograft from Deceased High Risk Donor and its impact on Risk for Delayed Graft Function (DGF) C1INH (Berinert® [human][C1INH])
HYPOTHESIS	Pre-operative, infusion of C1INH before allograft reperfusion and 24 hour post-transplant will improve early graft function and reduce the rate of DGF in patients receiving kidney allografts

	from bigh a	atal dagaaa	ad danar	lo o m o o mo o
CONFIDENTIAL	Clinh	(Berinert®) IR	I Study in	Kidney Transplant

RATIONALE Early graft function has a long-term effect on graft survival. Poor early graft function and DGF contributes to decreased short- and long-term patient and graft survival, increased incidence of acute rejection, prolonged hospitalization, and higher costs of
effect on graft survival. Poor early graft function and DGF contributes to decreased short- and long-term patient and graft survival, increased incidence of acute rejection, prolonged
graft function and DGF contributes to decreased short- and long-term patient and graft survival, increased incidence of acute rejection, prolonged
decreased short- and long-term patient and graft survival, increased incidence of acute rejection, prolonged
and graft survival, increased incidence of acute rejection, prolonged
of acute rejection, prolonged
hospitalization and higher costs of
mospitalization, and might costs of
transplantation. Although multiple
factors contribute to the impaired graft
function, ischemia-reperfusion injury
(IRI) is the underlying pathophysiology
leading to poor early graft function and
DGF. A >35% incidence of DGF has
remained constant over time despite
significant improvements in
immunosuppressive strategies and patient
management. This may be due to
increased use of kidneys from "extended-
criteria" and/or non-heart-beating
donors, where even greater rates (>60%)
of DGF have been reported.
More than 96,680 people are currently
waiting for a kidney transplant in the
United States (UNOS.org 3/22/13). Of
the 15,092 kidney transplants performed
in the US in 2011, ~11,000 (62%) were
from deceased donors. Of these,
approximately 17% were from expanded-
criteria donors. The USRDS reports that
more than 50% of patients on the waiting
list are willing to accept a kidney from
an expanded-criteria donor (ECD) or DCD
donor.
NUMBER OF 70 patients will be enrolled into the
PATIENTS AND study (35 C1INH and 35 Placebo). The
CENTERS study will be initiated at Cedars-Sinai
Medical Center and extended to
collaborators with completion of
contractual agreements.
<pre>INVESTIGATOR / [name].</pre>
CLINICAL Cedars-Sinai Medical Center
TRIAL LOCATION

CONFIDENTIAL	C1INH	(Berinert®)	IRI	Study	in	Kidney	Transı	plant

CONFIDENTIAL	C1INH (Berinert®) IRI Study in Kidney Transplan
STUDY OBJECTIVES	 To evaluate and compare the safety of Berinert® 50U/kg in recipients of a kidney allograft from a high risk deceased donors receiving one IV dose of Berinert® 50U/kg (round to the nearest 500unit) or placebo preoperatively and a repeat dose (Berinert® 50U/kg v. Placebo) 24 hrs. post-transplant. To evaluate early kidney function in recipients of a kidney allograft from a high risk deceased donors following the administration of two IV doses of Berinert® pre-operatively and 24 hrs later as compared to placebo.
STUDY DESIGN	Patients who fulfill all I/E criteria will be enrolled into Study I Study Group (70 patients): Treatment Arm I - Patients will be administered one IV dose of 50U/kg of Berinert® (round to the nearest 500unit) on-call to OR for kidney transplant. Control Arm - Patients will be administered one IV dose of normal saline (NS) approximately on-call to the OR for kidney transplant in a volume identical to the volume of the IV dose of Berinert®. Berinert® (50U/kg) round to the nearest 500unit) or placebo will be administered to study subjects again at 24 hrs post-transplant.
STUDY POPULATION	 Inclusion Criteria: Adult men or women (18-70 years of age) who are on chronic dialysis therapy and acceptable candidates for receipt of a kidney transplant. Recipients of kidney allograft from ECD donors Recipients of kidney allograft from DCD donors

- Recipients of kidney allograft other than ECD and DCD who have risk index of 3-8 (minimum 3 and maximum 8) for DGF, based on the criteria in the risk index detailed in the table below
- Recipients who are ABO compatible with donor allograft
- Pre-transplant vaccination with Menactra® meningococcal vaccine
- Understand and sign a written inform consent prior to any study specific procedure

Women of childbearing potential must have a negative pregnancy test prior to randomization, and must be on an acceptable form of birth control.

Characteristic		Index
	VT2Y	THUEX
Donor Age (years)		
<40		0
41-49		1
50-54		2
55-59		3
>60		6
Cold Ischemia time		
0-12		0
13-18		1
19-24		2
24-30		3
31-36		4
>37		6
Recipient Race		
Non-Black		0
Black		1
Recipient with Diabetes		
Has diabetes		1
No diabetes		0
Donor Death due to CVA		-
Donor age < 50 years		0
Donor age >50 years		3

Exclusion Criteria:

 Patients with a known prothrombotic disorder. (eg. Factor V Leiden)

CONFIDENTIAL C11	INH (I	Berinert®)	IRI	Study	in	Kidney	Transplan	t
------------------	--------	------------	-----	-------	----	--------	-----------	---

• Patients with a history of thrombosis or hypercoagulable state, excluding access clotting. • Patients with a history of administration of C1INH containing products or recombinant C1INH within 15 days prior to study entry. • Patients with a known hypersensitivity to treatment with C1INH. • Patients with an abnormal coagulation function. (INR >2, PTT> 50, PLT<80,000) who are not on anti-coaqulation. • Patients with known active presence of malignancies. • Patients who are PCR positive for Hep B, Hep C, or HIV. • Recipients of pre-emptive kidney transplantation. • Recipients of multi-organ transplants. (kidney and any other organ) • Recipients of kidney allograft from DD who: CIT < 18 hours, terminal serum creatinine $\leq 1 \text{mg/dl}$. • Recipients of kidney allograft that was on pump preservation for any period prior to transplantation. • Recipients of kidney allograft from a living donor. • Female subjects who are pregnant or lactating. STUDY ENDPOINTS SAFETY: • Overall incidence of adverse events and serious adverse events and relationship of AE and SAEs to the study treatment Evaluation of blood chemistry, hematology, and coagulation

parameters

- Patient and graft survival at Day
 90
- Rate of acute cellular rejection (ACR) and antibody mediated rejection at Day 90

EFFICACY ASSESSMENTS:

Primary Endpoints

For patients who do not require dialysis in the first 7 days:

- Proportion of patients enrolled with serum creatinine >3mg/dL on postoperative day 5.
- Proportion of patients with serum creatinine reduction ratio of < 30% from 24 to 48 hours post-transplant.

For patients who require dialysis in the first 7 days: (Excluding patients who get dialysis for hyperkalemia)

- The proportion of patients enrolled who require at least one session of dialysis in the first 7 days post transplant.
- Number of dialysis sessions per patient in the first 7 days post transplant.

Secondary Endpoints

- Daily serum creatinine for seven days post transplant or until discharge.
- Daily Calculated Creatinine Clearance for seven days post transplant or until discharge.
- Serum creatinine at 14, 28, 60, and 90 days post transplant.
- Total 24 hr urine output days 1-7 post-transplant.
- Rate of dialysis use at 14, 28, 60, and 90 days post transplant.

- Dialysis duration at 14, 28, 60, and 90 days post transplant.
- Rate of acute cellular and antibody mediated rejection episodes by day 90.
- Patient and graft survival by day 90.
- Calculated creatinine clearance at 14, 28, 60, and 90 days post transplant.
- Incidence of DGF as categorized by a DGF scale of increasing severity as follows:
- Grade 1 immediate urine production and no need for dialysis with creatinine reduction ratio (CRR) between time 0 of transplantation and day 7 post-transplantation >70%
- Grade 2 creatinine reduction ratio (CRR) between time 0 of transplantation and day 7 post-transplantation of >70% with need for dialysis
- Grade 3 creatinine reduction ratio (CRR) between time 0 of transplantation and day 7 post-transplantation <70% with no need for dialysis
- Grade 4 creatinine reduction ratio (CRR) between time 0 of transplantation and day 7 post-transplantation of <70% with need for dialysis.
- Protocol biopsies will be performed at the time of implantation.
 Pathological analysis will be done to determine if there is an increase in interstitial

CONFIDENTIAL	C1INH (Berinert®) IRI Study in Kidney Transplant
	fibrosis/tubular atrophy (IFTA), glomerulosclerosis, transplant glomerulopathy, and other markers of ischemic injury.
IMUNOSUPPRESSION REGIMEN	 Induction therapy using Thymoglobulin in divided doses for a total of 6mg/kg or Campath 1H 30mg SQ x 1. Calcineurin inhibition (Tacrolimus or Cyclosporine) will be delayed for minimum 24 hours post transplant. MMF will be started and used per standard of care (SOC). Corticosteroids will be used per SOC. Valgancyclovir will be used as the prophylaxis for CMV for a minimum of 6 months. Prophylaxis for bacterial and fungal infection will be per institutional SOC. Diagnosis and treatment of acute cellular or antibody-mediated rejection will be per institutional SOC.
STATISTICAL	Descriptive and comparative statistics
ANALYSIS	will be used to evaluate results
DURATION OF STUDY	90 days

3. Investigator(s) And Other Study Participants

Information regarding additional key personnel involved in the conduct of the study, including names and contact details of participating investigators, monitors, clinical laboratories, technical departments and/or institutions, as well as information on members of additional study committees, will be found in the study files of the sponsor and on site if requested.

A Data Safety Monitoring Board (DSMB) committee will review safety data. Quarterly assessment of AEs & SAEs will be performed and reported to CSL Behring, FDA and Cedars-Sinai IRB. In addition, DSMB must be informed and may be convened at any time questions about safety arise and/or thromboembolic events

occur. Please see appendix E for DSMB charter and FDA Guidance for Clinical Trial Sponsors.

4. Investigational PlanStudy Design And Plan

This is a Phase I/II double-blind, randomized, placebo-controlled study assessing safety and limited efficacy of intraoperative C1INH (50U/kg) vs. Placebo administered prior to graft reperfusion in adult subjects receiving a deceased donor kidney allograft considered high-risk for development of DGF. Patients will also receive an additional dose 24 hrs. post-transplant (C1INH (50U/kg vs. placebo). Once eligible patients are identified, consented, and have an acceptable kidney transplant offer, they will be randomized by the Cedars-Sinai Research Pharmacy to receive study drug vs. placebo. Drug and placebo will be prepared by the Cedars-Sinai Research Pharmacy and conveyed to the operating room in a blinded manner.

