4.1.1 Study Drug Administration Timing

In consideration of the latest time point of treatment application before graft reperfusion (ie. beginning of renal vein anastomosis), study treatments will be administered preoperatively at any one point in time, from time of admission up to the beginning of renal vein anastomosis **before graft** reperfusion. Due to the biologic half-life of C1INH (approximately 2.5 to 3.8 days), the time difference between early and late intraoperative treatment application, is thought to be negligible. In addition, the patients will receive study treatments at 24 hrs. post-transplant. This will constitute the entirety of C1INH vs. placebo administration. The study format is shown below in figure 3.

[figure not shown]

Figure 3: Study format to evaluate C1INH in DGF.

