4.6.1.2 Secondary Efficacy Endpoints

- Daily serum creatinine for seven days post transplant or until discharge.
- Daily Calculated Creatinine Clearance for seven days post transplant or until discharge.
- Serum creatinine at 14, 28, 60, and 90 days post transplant.
- Total urine output in hours 16-24, 40-48 post transplant.
- Rate of dialysis use at 14, 28, 60, and 90 days post transplant.
- Dialysis duration at 14, 28, 60, and 90 days post transplant.
- Calculated creatinine clearance at 14, 28, 60, and 90 days post transplant.

CONFIDENTIAL

- Rate of acute cellular and antibody mediated rejection episodes by day 90.
- Patient and graft survival by day 90.
 - Protocol renal transplant biopsy at time of implantation.
 - Incidence of DGF as categorized by a DGF scale of increasing severity as follows:

Grade 1 - immediate urine production and no need for dialysis with creatinine reduction ratio (CRR) between time 0 of transplantation and day 7 post-transplantation >70%

Grade 2 - creatinine reduction ratio (CRR) between time 0 of transplantation and day 7 post-transplantation of >70% with need for dialysis

Grade 3 - creatinine reduction ratio (CRR) between time 0 of transplantation and day 7 post-transplantation <70% with no need for dialysis

Grade 4 - creatinine reduction ratio (CRR) between time 0 of transplantation and day 7 post-transplantation of <70% with need for dialysis

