Appendix A

Study visit										
	Screening	Transplant Day 0 (Infusion #1 C1INH vs Placebo)	Day 1±6 hrs (Infusion #2 C1INH vs Placebo)	Day 2±6 hrs	Day 3±6 hrs	Day 4±6 hrs	Day 5±1 days	Day 6±2 days	Day 7±3 days *	Day 14 ±3 days
Informed Consent	Х									
Inclusion/exclusi on criteria review	^ X									
Medical History	X									
Complete Physical Exam (Including DVT Exam) (1)	X	X	X	X	Х	X	X	X	x	
Vital										
signs/weight	Χ	Х	X	Х	Х	Х	Х	Х	Х	Х
12-lead ECG (w/in 6M)	Х									
Chest X-ray (w/in 6M)	Х									
Safety laboratory tests (CBC, CMP)	X	Х	Х	Х	х	Х	Х	Х	Х	Х
PT, PTT, D. Dimer, Fibrinogen	Х	Х	Х						Х	
Review Historical Serologies for HIV, HBV, HCV, CMV and EBV	X									
Pregnancy test (for WOCP)	X									
Urinalysis	Х									Х
Urine Output		v	v	V	V	Х	V	Х		
Measurement Estimated GFR (using MRDR or Cockroft & Gault		X	X	X	X		X		X	
equation)			Х	Х	Х	Х	Χ	Х	Х	Χ

OOMITEDENTIA		OTTIVII (DCI	ernerco, in	1 Deady	±11 1(±0	11101 11	amopia			
Allograft biopsy		Х								
Dialysis	1		+	+						
Assessment	ı	X	X	Х	Х	Х	Х	Χ	х	Х
Assessment for					1					
DVT (Using Wells	ı									
Criteria Score)	ı									
(2)		X	Х						Х	
Pneumococcal	ı									
Vaccine &	ı									
Neiserria	ı									
Menigitides	Х				 				 	 
Berinert® vs	ı									
Placebo Infusion	ı									
_		X	Х		 	 	 	  '	 	1
C3, C4 Levels		Χ	Х		 	 		'	Х	
C1 Inhibitor				T						
Level (Prior to	1									
each infusion)		Χ	X						Х	
Campath or	1									
Thymoglobulin	ı									
administration	 	X			 		 		 	
Concomitant	ı									
medications	Х	X	Х	Х	X	Х	Х	Χ	Х	Х
Adverse Event	ı									
Monitoring	ı		X	Х	X	Х	Х	Х	Х	Х
Acute Rejection										
Assessment	1									

- (1) DVT exam will be done on day 0 and day1 (days Berinert vs.Placebo are given)
- (2) For scores indicating high risk for DVT, patient will have Doppler ultrasound.

*Day 4-7 assessments should be performed daily until the patient is discharged.

**If patient is discharged prior to day 7, day 7 lab assessments should be performed.

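### The implantation biopsy cannot measure an increase in chronic lesions or show efficacy on them; those readings belong with the baseline characteristics

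*Combined protocol and SAP*

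**What the plan says.** Section 2.2, under the secondary efficacy endpoints, states: "Protocol biopsies will be performed at the time of implantation". It gives the purpose as follows: "Pathological analysis will be done to determine if there is an increase in interstitial", continuing after a page break with "fibrosis/tubular atrophy (IFTA), glomerulosclerosis, transplant glomerulopathy, and other markers of ischemic injury". Section 4.6.1.2 repeats the item under Secondary Efficacy Endpoints as "Protocol renal transplant biopsy at time of implantation", with no variable, scale or comparator. Section 2.1 gives the same timing: "We will also evaluate biopsies at transplant in all entered patients". In Appendix A the row "Allograft biopsy" has one visible mark, under Day 0.

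Section 4.1.1 places the first infusion "from time of admission up to the beginning of renal vein anastomosis", that is, before reperfusion. It then adds that "the patients will receive study treatments at 24 hrs. post-transplant".

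No analysis of the biopsy is described. The synopsis promises only descriptive and comparative statistics in general terms, and section 6.1 is a heading with no content in the available text.

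**The concern.** An increase is a change between two measurements, and the plan describes one. A comparison between arms does not repair this for interstitial fibrosis/tubular atrophy (IFTA), glomerulosclerosis and transplant glomerulopathy. These are chronic lesions, and whatever is seen in them at implantation reflects the donor kidney, not the study drug.

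Two things are at stake:

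- **Interpretation.** An imbalance in donor quality could be read as a drug effect because the plan files the measurement under efficacy. This matters more here because 2.1 makes the choice of a Phase III endpoint a secondary objective, and a measure that cannot respond to treatment should not be a candidate.
- **Lost information.** The introduction names donor tissue quality as a risk factor for DGF. The trial mixes extended-criteria, cardiac-death and risk-index kidneys with only 35 patients per arm, so chance imbalance in donor quality is plausible. The biopsy would describe that imbalance, yet the plan does not use it as a baseline variable.

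**Working it through.** The plan gives no effect size, power or significance level for the biopsy, so there is no figure to reproduce. The check sets the sections side by side.

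**1. How many protocol biopsies are there?** Sections 2.1, 2.2 and 4.6.1.2 and Appendix A all place the biopsy at transplant or implantation. The visit lists in 4.6.3.3 to 4.6.3.5 (Days 1-7, 14/28 and 60/90) contain none. Day 90 has a rejection assessment, but rejection is diagnosed under institutional standard of care. Any for-cause biopsy would be selective and could not serve as protocol follow-up.

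**2. Can an increase be estimated?** Change values per patient = protocol biopsies − 1 = 1 − 1 = 0. Over 70 patients that is 70 × 0 = 0 change values.

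**3. Can the arms be compared on chronic lesions?** Dose 1 is given before reperfusion (4.1.1, 4.5.4.1, 4.5.9), and dose 2 comes 24 hours after transplant, so after an implantation biopsy. Let X be a chronic-lesion score in that sample. On the premise that chronic lesions do not form or regress in the short time between dose 1 and the biopsy, X is a donor characteristic. Randomisation then gives E[X | C1INH] − E[X | placebo] = 0. A statistically significant difference would be a type I error.

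**4. Does the same hold for the remaining item, the markers of ischemic injury?** Not necessarily. It depends on when the sample is taken:

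| Biopsy relative to reperfusion | Chronic lesions | Acute ischemic markers |
|---|---|---|
| Before | Donor characteristic | Pre-exposure: the graft has not yet met the recipient's blood |
| After | Donor characteristic | Post-treatment: an early arm difference is possible in principle |

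The documents do not say which row applies.

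**5. Illustration of false-positive risk.** Assume, as the plan does not specify, three independent tests at 5%, one per named chronic lesion. The chance of at least one significant result with no true effect is 1 − 0.95³ = 1 − 0.857 = 0.143. Counting only results that favour C1INH, it is 1 − 0.975³ = 1 − 0.927 = 0.073. Lesions read in the same core are unlikely to be independent, and without independence the upper bound is 3 × 0.05 = 0.15. The argument rests on step 3, not on these percentages.

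**The case against.** The strongest objection concerns scope. A reader might infer that the implantation biopsy can show no treatment effect of any kind, and that all of it should become baseline data. The documents do not support this. The endpoint also covers markers of ischemic injury, the item closest to the trial's hypothesis, and the first dose precedes reperfusion. If the sample is taken after reperfusion, acute markers are post-treatment measurements. Calling them baseline would be wrong, and adjusting for them could remove part of any drug effect. This objection stands and limits the point to the chronic lesions.

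A second objection is that the record is incomplete. The visible part of Appendix A stops at Day 14 of a 90-day study, and Figure 3 is not shown. The silence of the visit lists is also weak evidence: the Day 0 list in 4.6.3.2 omits the biopsy that Appendix A marks on that day. So it is fair to say that no other protocol biopsy is described, but not that none exists. The endpoint wording itself still refers only to implantation.

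A third objection is that no significance test on these lesions is prescribed. It would therefore be speculative to say that a difference will be reported as efficacy, or that the trial carries a 14% error rate. That is correct. The documents show only that the item is classed as efficacy and that nothing in the plan rules out such a reading.

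Finally, this is one of many secondary endpoints in a study that says it mainly explores safety. That limits the importance of the point but does not remove the inconsistency.

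**Conclusion.** The point holds for the chronic lesions. From the biopsy as described, no increase can be measured, and the expected arm difference in IFTA, glomerulosclerosis and transplant glomerulopathy is zero. A difference in them would be chance imbalance, not efficacy.

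This rests on two assumptions: that no follow-up protocol biopsy sits in the parts of the schedule that are not visible, and that chronic lesions do not change between the first dose and an implantation sample. For acute ischemic markers the question stays open until the timing relative to reperfusion is stated.

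The size is modest. One secondary endpoint is misclassified and a useful baseline measure is unused. The primary endpoints and the sample size are untouched. The 14% figure should be left out of any summary, or labelled as resting on three independent 5% tests that the plan does not contain. The change should be made because it alters what the trial can claim and uses data already being collected.

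**What to change.** In 2.2 and 4.6.1.2:

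- Delete the reference to an increase.
- Move IFTA, glomerulosclerosis and transplant glomerulopathy from the efficacy endpoints to the baseline characteristics, reported by arm and without an efficacy interpretation.
- Name a scoring scale, and prespecify the resulting chronic-injury score as a covariate in a supportive adjusted analysis of DGF, stating which DGF definition it uses.
- State whether the biopsy is taken before or after reperfusion. Only if it is after, keep acute ischemic-injury markers as a separately defined exploratory comparison between arms. Do not use those acute markers as a baseline covariate.

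If later columns of the schedule do contain a follow-up biopsy, the endpoint should instead name it and define the change to be analysed.

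The cost is small but goes beyond wording. The chronic lesions are lost as a secondary endpoint, a scale has to be chosen, and a short model specification has to be written. No procedure is added.
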